9.3.1. Timing of consent

Trial consent must be obtained at the baseline visit before any trial specific procedures are undertaken.

9.3.2. Loss of capacity

Loss of mental capacity of a participant after giving informed consent for the trial is expected to be a rare occurrence. Should this occur it should be reported to CTRU via a withdrawal form with no further trial procedures or data collection occurring from this point. Any data collected up to the point of withdrawal will be kept on record and used in the trial analysis.

9.4. RANDOMISATION

Participants who have confirmation of eligibility and written informed consent will be randomised into the trial by an authorised member of staff at the trial research site.

Participants will be randomised on a 1:1 basis between KJD (Intervention) and KR (control). Randomisation will be based on a minimisation algorithm with random component stratified by delivery unit (Section 8.2.1) and OA severity (Kellgren-Lawrence Grades 2-3 vs. Grade 4 (Appendix 1)) (17).

Since KJD is not a standard technique only some participating surgeons will have the required experience of this procedure. Additionally, some surgeons may not be in individual equipoise despite there being centre equipoise. A hybrid expertise based design (18) where surgeons are categorised into delivery units allows the trial to be feasible and pragmatic.

9.4.1. Timing of randomisation

Randomisation should take place on the same day as the baseline visit, which can be up to 6 weeks before the planned date of surgery. The range of movement and timed up and go tests should be performed and all baseline questionnaires completed BEFORE the participant is randomised (see Section 12 for further details of baseline assessments).

9.4.2. Randomisation process

Randomisation will be performed centrally using the CTRU automated secure 24-hour randomisation service which can be accessed via the web or telephone. For web and telephone randomisation the same site code, authorisation code/site staff email address and PIN used for registration will be required to access the system. The person telephoning or accessing the web address to randomise the participant must completed the Randomisation CRF available have at the time of telephoning/accessing the web as the following information will be required:

- Site code
- Details of intended delivery unit
- Participant details, including initials and date of birth
- Confirmation of informed written consent

- Confirmation of participant's eligibility for the trial
- Confirmation of completion of TUG test and ROM
- Confirmation of completion of baseline participant questionnaires

Direct line for 24-hour randomisation: [name]

Web address for 24-hour randomisation: https://lictr.leeds.ac.uk/webrand/

Participants may only be randomised into the trial by an authorised member of staff at the trial research site, as detailed on the Authorised Personnel Log.

After trial randomisation the research site will:

- Add the unique participant ID number to all CRFs and participant consent and contact details forms.
- Return a copy of the completed consent and contact details forms to CTRU
- Book/confirm the surgery and advise the participant of the randomisation allocation and date of planned surgery. Surgery should take place within 6 weeks of the date of randomisation.
- Notify the participant's GP of their participation in the trial using the approved KARDS GP Letter.

Following randomisation, CTRU will email a Participant Randomisation Notification to the research site.

10. INTERVENTION DETAILS

10.1. PRE-OPERATIVE

Pre-operative preparation (e.g. weight loss advice, physiotherapy) will be provided to all trial patients in line with the site's usual protocol for KRs.

10.2. ADMISSION

All trial participants will be admitted on the day of surgery or the previous night and should receive MRSA decolonisation and pre-operative assessment and optimisation as per local practice.

10.3. SURGERY

Surgical consent will be reconfirmed on the day of surgery and participants will be assessed by the clinical team (anaesthetist, and surgeon and/or their assistant) as per standard of care prior to proceeding with surgery.

In the case of single delivery units, patients will be operated on by a surgeon authorised to deliver one type of surgery (KJD or KR as relevant). In the case of dual delivery units, patients will be operated on by the intended surgeon regardless of their randomised allocation.

A surgical manual will be provided detailing the surgical procedures for both interventions and highlighting mandatory components.

10.3.1. Knee joint distraction

A definitive external fixator construct should be used which allows for controlled linear distraction across the knee joint of 5mm along the mechanical axis of the limb. The exact nature of the construct will depend on the equipment available at the site and surgeon preference. A list of permitted devices will be detailed in the surgical manual, and sites wishing to use devices not appearing on this list must provide CTRU with details of their preferred construct during site feasibility for prior approval. All equipment used must be CE-marked and intended to be used for distraction.

During surgery, the external fixation frame should be assembled according to this manual, with a focus on meticulous pin insertion to minimise the risk of complications. Fluoroscopy will be used to assist correct pin placement. Once the assembly is complete, 2mm of axial distraction (measured at frame) should be applied across the knee joint.

The limb should then be cleaned and a final check made for soft tissue tension around fixation elements with further skin releases made as required. Pin-sites should be dressed with an absorbent non-shedding dressing. Clips and bungs are available with various systems to keep these in place and apply gentle pressure.

10.3.2. Knee replacement surgery

Knee replacement surgery will be performed in line with local practice. Surgical steps will vary depending upon type of implant and surgeon preference but mandatory

components will be highlighted in the surgical manual. The surgeon performing the procedure is expected to be familiar with and follow the specific surgical steps for the implant being used as detailed in the instructions for use document provided by the manufacturer.

10.4. POST-OPERATIVE CARE

10.4.1. All participants

Routine general post-operative care will be employed in line with local site protocols. Participants can be mobilized on the first day post op under physiotherapy supervision. Full weight-bearing as pain allows is permitted. Participants can be discharged as soon as they are fit to return home, in line with local practice.

Standardised x-rays (AP and lateral views) will be taken according to a radiography manual which will be provided to sites.

10.4.2. Up to 7 days post operation (KJD only)

A further 1mm of distraction will be applied per day for three days to create a total of 5mm articular distraction at the frame. This can be done in hospital or by the participant at home, following instruction, as preferred. At day 3 the participant will have a standardised AP and lateral x-ray to confirm the distraction at the joint (see radiography manual for further details).

If distraction at the joint is less than 5mm at day 3 the frame will continue to be distracted by 1mm a day until 5mm of distraction at the joint is confirmed radiographically, or up to a maximum of 7 days in total.

10.4.3. Fixator removal (KJD arm only)

External fixators will be removed under general or regional anaesthesia at Week 6 after placement, as detailed in the surgical manual. Standardised AP and lateral x-rays will be taken before the frame is removed, as detailed in the radiography manual.

Participants will be admitted as day case patients with appropriate preparation for anaesthesia according to local protocols. Following administration of anaesthesia, all dressings will be removed. The external fixator assembly will be removed leaving the pins in place. The pin-sites will be cleaned thoroughly and the pins will then be removed by hand. Pin-sites must be left open and covered with adhesive dressings.

A gentle manipulation under anaesthesia (MUA) to achieve at least 0 to 90 degrees of motion should then be attempted. Once recovered from anaesthesia the participant will be allowed home, usually the same day.

Pin-sites will be kept covered until they have healed and immersion in water avoided. Participants are generally permitted to shower as long as the pin-sites are covered.

10.5. ADDITIONAL INTERVENTIONS

During the course of follow up participants may require further intervention for symptomatic knee OA as per routine NHS practice. Further clinical intervention is permitted for all participants and recorded as part of the trial.

10.6. CONCOMITANT TREATMENTS

Decisions about concomitant medications/treatments for symptomatic knee osteoarthritis will be according to the local medical plan and clinical management.

11. OUTCOME MEASURES

The trial will follow the recommendation to report a range of patient reported outcome measures (PROMs) and clinical experience to observe consistency across measures (19).

11.1. PRIMARY OUTCOME MEASURE

The primary outcome measure is the KOOS pain score within 12-months from surgery.

The Knee Injury & Osteoarthritis Outcomes Score (KOOS) is a patient-administered questionnaire, validated for use in patients with knee OA or knee injury (20). It consists of 5 domains: Pain, other Symptoms, Function in daily living (ADL), Function in sport and recreation (Sport/Rec) and knee related Quality of life (QOL). It is recommended as the PROM of choice for assessment of patients with knee OA by the International Consortium for Health Outcomes Measurement. It typically takes 10 minutes to complete. It has been used in many RCTs comparing outcomes of knee OA treatment (21–23). For the purpose of an RCT, KOOS subscale scores are recommended to be

used as the primary outcome (24). A total KOOS score has not been validated and is not recommended.

The primary outcome measure is the KOOS pain component, given pain was indicated by the PPI group as being the most important outcome. In patients with severe knee OA, pain refractory to conservative treatment is the primary indication for a surgical intervention. Knee pain associated with OA typically continues to improve for the first 12 months after an intervention and then plateaus (25). Hence the KOOS, and other outcome measures, will be requested to 24-months post-surgery.

The previous week is the time period considered when answering the questions. Standardised answer options are given (5 Likert boxes: None, Mild, Moderate, Severe, Extreme) and each question is assigned a score from 0 to 4. A normalized score (100 indicating no symptoms and 0 indicating extreme symptoms) is calculated for each KOOS domain.

11.2. SECONDARY OUTCOME MEASURES

1. Patient reported outcomes and quality of life outcomes

a) KOOS (At component level)

KOOS domains (except pain): other Symptoms, Function in daily living (ADL), Function in sport and recreation (Sport/Rec) and knee related Quality of life (QOL).

b) Pain VAS

The pain VAS is a unidimensional measure of pain intensity (26,27), which has been widely used in diverse adult populations, including those with rheumatic diseases (26,28–30). The pain VAS is a continuous scale comprised of a 10cm horizontal length ranging from "no pain" (score of 0) to "pain as bad as it could be" or "worst imaginable pain" (score 100 [100mm scale])

c) Oxford Knee Score (OKS)

OKS is a short, reproducible, valid PROM consisting of 12 items which provides an overall scale for assessing outcomes of knee interventions and is sensitive to clinically important changes (31–33). Each question is scored from 0 to 4 with 4 being the best outcome. This method when summed produces overall scores from 0 to 48 which reflects the severity of problems that the respondent has with their knee, with 48 being the best outcome (i.e. least symptoms). It takes approximately

5 minutes to complete the form. Whilst the applicability of the OKS to the general OA population is unclear, it is commonly used for joint replacement registries and is the outcome measure of choice of the National Joint Registry for England, Wales, Northern Ireland and the Isle of Man.

2. Objective assessment of knee function

- a) The active range of movement. Measured using a goniometer at 3, 12 and 24 months, the angles in degrees will be measured with the affected leg fully extended (extension) and fully bent (flexion), to determine the range of movement (i.e. the difference in angles between the two values, extension minus flexion). A flexion deformity will be measured as a positive value and hyperextension will be recorded as negative value.
- b) **Timed-up-and-go test**. Time in seconds for the participant to rise from a chair, walk three meters, turn around, walk back to the chair, and sit down.

3. Incidence of complications

Intra-operative complications: Complications occurring during the initial trial operative procedure will be recorded.

This trial-specific questionnaire will measure participant's reported health care use, days off work and private costs due to knee OA using a bespoke short self-reported schedule adapted from forms already developed at the University of Leeds. Healthcare use includes the number of contacts with clinical staff (occupational health, primary care staff, rheumatologists etc.) and medications as a result of knee OA.

6. Implementation processes and intervention fidelity

Quantitative

Treatment fidelity will be assessed on the surgical CRF which will record whether the mandatory components of surgery were performed as detailed in the surgical manual and any deviations explained.

Post-operative x-rays (AP and lateral) will also be returned and assessed by central review.

Qualitative

Outcomes relating to the qualitative evaluation with surgical and clinical staff of intervention processes and qualitative fidelity are described fully in Section 16.

7. Qualitative evaluation of participant experiences

Outcomes relating to the qualitative evaluation of participant experiences are described fully in Section 16.

12. DATA COLLECTION

Participating sites will be expected to maintain a file of essential trial documentation (Investigator Site File), which will be provided by the CTRU, and keep copies of all completed CRFs for the trial. CRFs and participant-completed questionnaires will contain the participant's unique trial number, date of birth, and initials. Clinical data will be collected at baseline, on the day of surgery, up to day 7, week 6 (KJD only), and months 3, 12, and 24 post-surgery. Participant completed data will be collected at baseline, on the day of surgery.

12.1. SUBMISSION OF TRIAL DATA

Participating research sites will be expected to submit original paper CRFs to the CTRU at the University of Leeds and retain copies of all completed CRFs for the trial in the Investigator Site File. Following receipt, the CTRU will contact trial sites to resolve any missing or discrepant data. Any outstanding CRFs will be requested by the CTRU until received or until the data is confirmed as unavailable. All trial x-rays will be transferred to the CTRU using the secure file transfer service. For full details of the imaging requirements and process please refer to the radiography manual.

12.2. SCHEDULE OF CLINICAL ASSESSMENTS / DATA COLLECTION POINTS

TRIAL VISIT	1	2	3	4	5	6	7	8
Time from date of surgery	≤6 weeks before	0	Up to Day 7	Week 6	Month 3	Month 6	Month 12	Month 24
Time window	-	-	-	-	+/- 4 weeks	- 2 weeks + 6 weeks	+/- 6 weeks	+/- 8 weeks
Visit type	Baseline	Surgery	Post- operative	Fixator removal	Follow up (clinic)	Follow up (post / online)	Follow up (clinic)	Follow up (clinic)
Treatment group	All	All	All	KJD only	All	All	All	All
				Unity				
Confirmation of eligibility	Х							
Informed Consent	Х							
Patient demographics	Х							
Medical history	Х							
OA severity (Kellgren- Lawrence grade based on standard AP and lateral x-rays)	x							
Physical examination of knee	X°							
Range of movement using goniometer	х				х		х	х
Timed up and go test	Х				Х		Х	Х
Rosenberg view x-ray	Х				Х^		Х^	Х^
Weight bearing AP/Lateral view x-rays	X°		Х	Х^				
Participant completed questionnaires (KOOS, OKS, EQ5D-3L, Pain VAS, Health Resource Use)	х	X*			х	х	х	х
Randomisation	Х							
Surgery (KR or KJD)		Х						
Surgical details		Х		Х^				
Distraction of external fixator (KJD only)		Х^	Х^					
Removal of external fixator (KJD only)				Х^				
Complications		Х	Х	Х^	Х	Х	Х	Х
Additional knee related surgery		х	х	Х^	Х	Х	Х	Х
Concomitant medications	Х	Х	Х	Х^	Х	Х	Х	Х

° If not performed within last 6 months prior to baseline

OKS: Oxford Knee Score

* KOOS only, up to 1 day before surgery

^ KJD arm only

KOOS: Knee Injury and Osteoarthritis Outcome Score

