9.3. INFORMED CONSENT

Following information provision about the trial, all patients must be given the opportunity to discuss the trial with their family and healthcare professions before they are asked whether they would like to take part. Patients will be given as much time to consider their participation in the trial as possible; ideally a minimum of 24 hours, but this will not be imposed if a participant wishes to consent sooner, is fully informed about the trial and has had sufficient time to consider their participation. The right of a patient to refuse consent without giving reasons will be respected.

Assenting patients will be invited to a baseline visit up to 6 weeks before their planned date of surgery. At this visit they will be formally assessed for eligibility and invited to provide written informed consent for their participation in the trial, including explicit consent for the transfer of a copy of their signed consent form to the CTRU.

KARDS protocol v1.0_190927

Informed consent will be obtained by the Principal Investigator (PI) or an appropriate, delegated, healthcare professional (e.g. another participating surgeon or research nurse) who is GCP trained and has been approved by the PI as detailed on the Authorised Personnel Log.

The Principal Investigator (PI) retains overall responsibility for the informed consent of participants at their site. The PI must ensure that any person with delegated responsibility for the informed consent process is duly authorised, trained and competent to participate according to the ethically approved protocol, principles of Good Clinical Practice (GCP) and Declaration of Helsinki 1996.

A record of the consent process specifying the date of consent and those present will be detailed in the participant's hospital notes. The original consent form will be filed in the Investigator Site File at the hospital. A copy of the consent form will be given to the participant, a second copy filed in the hospital notes (as per local practice) and a third copy will be returned the CTRU at the University of Leeds.

Where a participant is required to re-consent or new information is required to be provided to a participant it is the responsibility of the PI to ensure this is carried out in a timely manner according to any timelines requested by the CTRU.

The participant must remain free to withdraw at any time from the trial without giving reasons and without prejudicing his/her further treatment/care.

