Adjusted estimates of the treatment effect will be estimated from multivariable regression modelling of the KOOS pain score at 12 months. Statistical significance of non-inferiority of KJD relative to KR will be based on a 2-sided likelihood-based test with a type 1 error of 2.5% in both tails, assuming KOOS pain scores (or transformed scores if appropriate) are normally distributed and adjusted by baseline score at the time of randomisation and stratification factors (delivery unit and OA severity). If the 95% confidence interval for the absolute difference in means between KJD and KR lies entirely below or includes the non-inferiority boundary (see Section 14.2) then there would be insufficient evidence to reject the null hypothesis that KJD is inferior to KR. Conversely, if the 95% confidence interval lies entirely above the non-inferiority boundary then there would be evidence to reject the null hypothesis and conclude KJD is non-inferior to KR. Further modelling will include confounders of age and BMI, observing and addressing non-linearity through use of fractional polynomial transformation. Secondary analyses of the primary outcome measure will be considered. If non-inferiority is demonstrated and KJD appears superior to the KR, based on estimated effect and CI, statistical significance for superiority will be calculated based on an ITT analysis with similar modelling strategy. A secondary analysis of the primary outcome measure will be based on random effects multilevel modelling to account for the nested and longitudinal structure of the data over the full 24 months follow-up.

ANALYSES OF SECONDARY OUTCOME MEASURES

Analysis of PROMs (KOOS components, OKS, Pain VAS and EQ5D-3L) will focus on reporting the pre-specified dimensions of the individual questionnaires. Questionnaire responses will be combined and transformed into dimension scores, according to scoring manuals where these exist, presented graphically and longitudinally. Standardised area under the curve statistics will be compared across treatment groups as an analysis conditional on patient survival.

Range of motion and timed up and go functional assessments will be reported descriptively.

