15. ECONOMIC EVALUATION

A within trial cost-effectiveness analysis within 24-months will be conducted adopting the perspective of the NHS and Personal Social Services. Costs and outcomes occurring beyond 12 months will be discounted at 3.5%. The primary outcome is Quality Adjusted Life Years (QALYs). The proposed methods for the economic evaluation follow the NICE reference case (46).

Health utility values will be estimated through administration of the EQ-5D-3L. Unit costs for health service resources will be obtained from national sources (e.g. Personal Social Services Research Unit [PSSRU] and NHS Reference Cost). The intervention cost will include theatre time, knee components used during the primary admission and during any knee-related readmissions or revisions.

The differences in mean costs and effects will be presented using incremental cost effectiveness ratio (ICER). Net incremental monetary benefit (NMB) will also be computed. The level of sampling uncertainty around the ICER will be determined using a nonparametric bootstrap to generate 10,000 estimates of incremental costs and effects. Bootstrapped estimates will be plotted on the cost-effectiveness plane to illustrate the uncertainty surrounding cost-effectiveness estimates (47). Bootstrapped estimates of cost and effects will also be used to compute the probability that each intervention is cost-effective for a range of cost-effectiveness thresholds. The results will be presented as cost-effectiveness acceptability curves (CEAC) (48).

In order to assess the long-term cost-effectiveness of KJD compared to KR, a decision analytic cost-effectiveness model will be used to estimate the likely impact on costs and benefits over 20 years. The model will be constructed and described in line with best practice (46). Data to populate the model will be derived from three sources:

1. The literature

2. Ongoing follow-up studies and clinical trials of Knee Joint Distraction as coordinated by UMC Utrecht (currently N=174 patients in follow-up with max 10 year follow-up, 105 started end 2017)

3. Publicly available UK orthopaedic registry data which will provide transition probabilities on knee replacement initial effects and longer-term effects.

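### EQ-5D-3L is not taken between baseline and month 3 in either arm, so utility during the six weeks in the fixator must be estimated, not measured

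*Protocol*

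**What the plan says.** The schedule in Protocol section 12.2 puts all self-completed instruments in one row, "Participant completed questionnaires (KOOS, OKS, EQ5D-3L, Pain VAS, Health Resource Use". The row is marked at baseline, at surgery and at months 3, 6, 12 and 24. A footnote limits the surgery entry: "KOOS only, up to 1 day before surgery". The cells for the days up to day 7 and for week 6 are blank in both arms. The month 3 visit has a window of 4 weeks either side. Baseline may itself precede surgery by some weeks (section 9.3): "Assenting patients will be invited to a baseline visit up to 6 weeks before their planned date of surgery".

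In the KJD arm the frame stays on for six weeks. Section 10.4.3 says "External fixators will be removed under general or regional anaesthesia at Week 6 after placement", followed by an attempted manipulation. Week 6 is a visit for that arm alone: section 12 lists "week 6 (KJD only), and months 3, 12, and 24 post-surgery", and in the schedule the week 6 cells for complications, additional knee surgery and concomitant medication are footnoted as KJD only.

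Section 15 makes QALYs over 24 months the primary outcome of the economic evaluation and states their source: "Health utility values will be estimated through administration of the EQ-5D-3L". For the PROMs, section 14.1 says "Standardised area under the curve statistics will be compared across treatment groups as an analysis conditional on patient survival".

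Sections 13.2, 13.2.2 and 13.2.3 require complications to be recorded however they come to light, from randomisation to the end of follow-up, with no distinction by arm.

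**The concern.** The largest short-term burden particular to one arm falls where utility is not observed. Only KJD participants spend six weeks in a fixator and have a second planned anaesthetic, and every scheduled EQ-5D-3L comes either before the frame goes on or at least three weeks after it comes off. Any QALY or area under the curve must bridge that interval from the readings on either side. If the bridge runs above the true course, and by more in the KJD arm than in the KR arm, the comparison leans towards KJD.

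This is a matter of data collection. The SAP or a health economics plan can choose how to bridge the gap, but cannot supply readings that were never taken. Later questionnaires do not help: section 11.1 gives KOOS a recall period of one week, so a month 3 form does not reach back to the frame.

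A smaller matter attaches to the same visit. KJD participants have a scheduled complication check at week 6 that KR participants do not.

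**Working it through.** The plan gives no figure for this point. The sample size (344) does not depend on it.

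**Length of the gap.** Month 3 is 3 × 52/12 = 13 weeks after surgery. With the window, the first postoperative EQ-5D-3L falls between 13 − 4 = 9 and 13 + 4 = 17 weeks. Counted from the baseline reading, the gap is up to 6 weeks longer. Readings during the six frame weeks: none. From frame removal to the first reading is 9 − 6 = 3 to 17 − 6 = 11 weeks, nominally 7.

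**Share of time.** The frame takes up 6/13 = 46% of the interval from surgery to month 3, but only 6/104 = about 6% of the 24 months over which QALYs are counted.

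**Effect on QALYs (illustration).** Let *d* be the amount by which utility in the frame lies below the straight line from baseline to month 3, net of the matching early shortfall in the KR arm. The protocol gives no utilities, so *d* is assumed. If the shortfall lasts exactly six weeks, the overstatement per KJD participant is *d* × 6/52. If it then tapers evenly to zero at month 3, the overstatement is *d* × (6 + 7/2)/52 = *d* × 9.5/52.

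| Assumed net *d* | Six weeks only | With taper to month 3 |
|---|---|---|
| 0.1 | 0.012 | 0.018 |
| 0.2 | 0.023 | 0.037 |
| 0.3 | 0.035 | 0.055 |

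If *d* is zero, because early recovery after KR is as poor as life in the frame, there is no bias in the comparison. If KR recovery is worse, the sign reverses.

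**Would one reading near week 6 help?** With a reading at week 6, straight-line interpolation gives a triangle of height *d* over 13 weeks: *d* × 13/(2 × 52) = 0.125 *d*. The true loss is 0.115 *d* (six weeks only) or 0.183 *d* (with taper). One reading therefore recovers the loss approximately in the first case and about two thirds of it in the second (0.125/0.183 = 0.68). Without it, none is recovered.

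**Complication checks after the day 7 period.** KJD: week 6 and months 3, 6, 12 and 24, which is five. KR: months 3, 6, 12 and 24, which is four. Between day 7 and month 3 the count is one against none. The text of section 12 leaves month 6 out of the clinical time points while the schedule marks it; the difference between arms is one check either way.

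**The case against.** Several stronger readings are tempting, and the protocol does not support them.

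- *That the QALYs leave out the frame weeks.* They do not. Those weeks would be estimated. Section 15 does not state the interpolation rule, so the straight line used above is an assumption about an unstated method.
- *That the bias in favour of KJD is established.* The early weeks after KR are equally unobserved, and only the differential shortfall matters. A deficit that lasts beyond frame removal would also lower the month 3 reading and so be partly captured. The direction is likely, from what only KJD participants undergo, but it is not shown.
- *That the loss can be put in money.* The euro threshold in section 5.1 describes an earlier cost-effectiveness result. Section 15 sets an NHS and Personal Social Services perspective and a range of thresholds, so a conversion at the euro figure would not be this evaluation's own.
- *That KR complications go unrecorded.* Week 6 is an operative visit that KR participants do not have, so recording events there is natural. Sections 13.2, 13.2.2 and 13.2.3 cover both arms throughout, section 13.2.4 requires the listed serious events within 24 hours, and month 3 checks everyone. What remains is possible under-recall of minor or transient KR events between day 7 and month 3.

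It is also fair to say that this is a choice of assessment frequency and not a contradiction, and that section 14.2 does not power secondary outcomes. None of this supplies the missing reading.

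**Conclusion.** The point holds as a limitation of the within-trial QALYs and of the areas under the curve for EQ-5D-3L, OKS and pain VAS: no reading is scheduled in either arm between surgery and month 3. The between-arm bias probably favours KJD. Its size is unknown; 0.012 to 0.035 QALY per KJD participant follows only if the net shortfall is 0.1 to 0.3 and lasts six weeks, and both are assumptions. The complication question is secondary and concerns evenness of ascertainment for minor events only. The primary analysis of KOOS pain at 12 months does not depend on any of this. The change is worth making because it is cheap and because the data cannot be recovered once a participant has passed week 6.

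**What to change.** Add EQ-5D-3L shortly before week 6 after surgery in both arms. Preferably use the same post or online route for everyone, so that mode does not differ by arm, and time it so that KJD participants answer while the frame is still on. Set a tight return window, equal in both arms. The reminder pattern in section 12.4, with a second posting or a switch to post at two weeks, is too slow here, since late answers would come from after frame removal. Amend the schedule in section 12.2 and the statement in section 12.4 that only month 6 is completed outside clinic. State that the new reading enters the QALY and EQ-5D area-under-the-curve calculations. OKS and pain VAS keep their gap unless they are added to the form.

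As a secondary step, put a brief complication and resource-use question to KR participants at the same contact. The site would follow up positive answers, because section 13.3 requires investigator judgement of causality.

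The cost is a protocol amendment and one short form per participant (section 11.2 puts EQ-5D-3L at about five minutes) through a route that already exists, with no extra visit. The downsides are some added burden and some non-response, which should be reported by arm.
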